Brief Acceptance-Based Retention Intervention for Newly Diagnosed HIV Patients

NCT04201288

Study Protocol – 8/30/21

BRIEF ACCEPTANCE-BASED RETENTION INTERVENTION FOR NEWLY DIAGNOSED HIV PATIENTS

Manual of Procedures (MOP)

INTRODUCTION

The Manual of Operating Procedures (MOP) has been compiled to assist study personnel in conducting the study “Brief Acceptance-Based Retention Intervention for Newly Diagnosed HIV Patients.” It documents study flow so that the screening, initial evaluation, enrollment, and follow-up of all study participants are conducted in a standardized manner. It details how data are to be observed, collected, and recorded, and specifies quality control procedures. The MOP defines methods for ensuring confidentiality of participant information.

This MOP serves as a supplement to the protocol and contains study conduct information in the form of administrative or detailed technical information that is not detailed in the protocol or protocol amendment. The MOP must be reviewed carefully in conjunction with the protocol by all study key personnel.

The MOP will be modified accordingly whenever a change in the protocol is approved or a study step has to be refined or re-defined for clarity and safety. The changes are captured by maintaining a version control numerically matching the progressing sequence of dates displayed on the cover page.

MOP CONTENTS AND ORGANIZATION

STUDY PROCEDURES

- A. [Responsibilities](#)
- B. [Training Plan](#)
- C. [Study Flow](#)
- D. [Screening and Eligibility Tracking](#)
- E. [Approaching/Assessing Patients](#)
- F. [Participant Payment \(ClinCards\)](#)
- G. [Baseline Assessment](#)
- H. [Post-Baseline Procedures](#)
- I. [REDCap Assessment Database](#)
- J. [Procedures for Withdrawal of Consent](#)
- K. [Procedure for when Patient Endorses Current Suicidal Ideation/Distress](#)
- L. [Safety Reporting](#)

A. RESPONSIBILITIES

The PI and investigative team are responsible for the implementation of the protocol, including:

[figure not shown]
- Participating in protocol finalization and preparing study materials
- Assuring that the study is conducted according to the protocol
- Identifying, recruiting, screening and enrolling participants
- Protecting participants' rights
- Obtaining informed consent from each participant
- Collecting study data and following participants through study completion
- Preparing recruitment and enrollment, gender and minority breakdowns, adverse event reports
- Assuring IRB review and approval
- Preparing and sending reports to the Data Safety Monitoring Board (DSMB)
- Preparing and sending annual reports to the funding agency, the National Institutes of Health (NIH)

B. TRAINING PLAN

The Research Assistant and Study Coordinator will be trained on all clinical assessments by the lead investigators. For all measures, the staff in training should familiarize themselves with the measures and complete mock interviews. The PI will lead all trainings on intervention and control condition delivery.

Interventionist training will include mock session practice and review of audio recorded sessions.

C. STUDY FLOW

D. SCREENING AND ELIGIBILITY TRACKING

How are potentially eligible individuals identified?

Intake nurses will reach out via email to notify when there is a new patient scheduled. We will find a convenient time during that appointment to approach the patient.

How is the screening conducted?

Study staff will use the screening form to determine eligibility.

How do we know which patients to approach for enrollment?

Staff use the following guidelines to determine whether patients are eligible or ineligible to be approached for study enrollment. The majority of the data to determine eligibility are available in the patient medical record; however, for any additional information not available in the medical record, the staff will need to consult with clinical intake staff.

A patient must meet all of the eligibility criteria listed below before they are approached about enrolling in the Engage study.

Table 1. Eligibility criteria

Inclusion Criteria	Exclusion Criteria

 • HIV+ • ≥ 18 years old • Entering HIV medical care services for the first time (that is, not transferring HIV care from another location) • Able to speak and read English at the level to be able to complete the study procedures • Have telephone access 	
 • Cognitive impairment that would interfere with adequate participation in the project (clinic staff will make this determination)

For

each patient screened on that day, the RA will enter the following information into the study Key file:

- ID: A unique screener ID will be generated for all individuals screened
- Date: Date screened

- Name: First *only*
- Telephone number: At least one contact number
- Permission to text appointment reminders: Yes / No
- Permission to leave voicemails for appointment reminders: Yes / No
- Permission to leave messages indicating research affiliation: Yes / No
- Age
- HIV status: Positive / Negative
- Cell phone: Yes / No
- Number of days in past 3 months when individual stopped using their cell phone

E. APPROACHING / ASSESSING PATIENTS

Before approaching the patient

Confirm with intake nurse via email that the RA will approach the new patient at their upcoming intake visit.

When heading to clinic, bring a clipboard with the:

- Screening form
- 2 copies of the consent form
- Release of Information form
- ClinCard FAQs and information documents
- Response cards set
- HIV education slides
- Mental health resources document
- Locator Form.
- Also bring a baseline questionnaire packet in case the patient immediately enrolls and wants to complete the baseline assessment while in clinic.

Remember, slides and consent show content related to the research study. Participants should be warned that these materials might reveal sensitive information. They can decline taking any of them.

Numbering system

Please use the following numbering system for identifying patients (PSID) and enrolling participants (SID): PSIDs=101-n; SIDs=1001-n

PSIDs should be assigned to every patient you identify and try to screen. That means that completed screens will not be continuously numbered – this is ok. The key is to assign a PSID to every new patient in the clinic.

Approaching the Patient

Patients are only approached and assessed during their free time during their clinical intake visit. Most staff are aware of this, but if the staff is not, please remind them that study staff are to only meet with patients during their free time.

Once you have met the patient, introduce yourself and ask if they have a few minutes to talk to you about an ongoing research study at the clinic. If they agree, administer the screener, which includes a brief recruitment script.

Patient consent

If a patient agrees to participate in the study, the staff will guide the patient through the consent form, answer any questions, and ask the patient to sign a copy of the consent form for our records.

After signing the consent form, the patient will need to complete the following:

- Engage Contact Locator Form

After completing these forms, the staff will set up a time to complete the baseline assessment with the patient later that day (if possible) or within 1 week.

Record all patient approaches in the “Key – HIV Engage” tracking file

F. PARTICIPANT PAYMENT (ClinCards)

Participants will be paid \$25 for completion of baseline and each follow-up assessment. They will not be paid for completing sessions with study interventionists. ClinCards will be used for all participant remuneration. These are MasterCards that function as reloadable debit cards.

Once the baseline appointment is completed, open up a ClinCard envelope and show the participant the card. Make note of the “Token” number, which is visible through the clear window on the front of the envelope. This links the participant to the specific ClinCard. As ClinCards are distributed, make note of the token number in LSUHSC’s tracking log and share the participant ID – token number assignment with PI [name]. Review the Participant ClinCard Information sheet and the FAQ document with the participant.

Highlight each section of the FAQ sheet, in particular noting:

- The 3-ish business days for payment to load onto the card (at baseline, the ClinCard already has \$25)
- How to set up a PIN
- When additional fees could be incurred
- What to do if the card is lost

At follow-up assessments, PI must initiate the upload of additional funds through Brown University. At the conclusion of follow-up assessments, inform the participant that their ClinCard will be loaded with an additional \$25 within 2-3 business days. Immediately contact PI at the conclusion of the assessment via email to ask him to initiate the reload process. He will then contact the relevant Brown University staff. Use the following template:

Email to PI as follows:

Subject Line – Grant: GR5271057

Hello,

Please approve my ____ AM/PM interview with Subject ID # XXXX in the amount of \$25 for Month, Day, Year on grant #GR5271057

Lost ClinCards

We will give participants the benefit of the doubt if they report losing their ClinCard. If a lost or missing ClinCard is reported, immediately inform PI so that he can cancel the lost card and prevent misuse of funds. A replacement ClinCard will be given one time to participants; if they lose >1 ClinCard, all additional ClinCards will be loaded with a reduced amount to cover the expense of the

replacement card. All replacement ClinCards must be given in-person to the participant.

G. BASELINE ASSESSMENT

The baseline interviews should be completed in a private interview room in the clinic or research offices. All interviews will be audio-recorded.

Baseline Assessment Schedule:

Interviews	Self-Reports (if possible)
Sociodemographics	Contemplation Ladder
Thoughts about PrEP	PROMIS Global Health Scale
Alcohol Use Disorders Identification Test (AUDIT-3)	Health Information
Addiction Severity Index Drug Module (ASI)	Well-Being Scale
Patient Health Questionnaire-9 (PHQ-9)	Impulsivity Scale
Disclosure Scale (BHD & SSSES)	Acceptance and Action Questionnaire-II (AAQ-II)
Disclosure List	Multidimensional Scale of Perceived Social Support (MSPSS)
COVID-19 items	Berger HIV Stigma Scale
	Healthcare System Distrust Scale
	Everyday Experience of Discrimination Scale
	Patient Satisfaction Survey

After the interviews are completed, allow the patient to complete the self-report measures independently (*if possible*). Briefly go over the self-reports with the patient, and ask if they have any questions. **Print all self-reports ONE-SIDED.**

In some cases, participants will consent to be in the study, but will leave the clinic before a baseline appointment can be started and/or completed. If this is the case, arrange a time for them to come complete the baseline appointment within 1 week.

H. POST-BASELINE ASSESSMENT PROCEDURES

After the baseline has been completed, check-in with the PI to verify the patient's eligibility for enrollment and for any questions in assessment/coding that may have arisen. If the PI agrees that the patient is eligible, and no problematic secondary characteristics have been identified that may hinder the patient's participation in the study, the patient is officially enrolled into the study.

Randomization:

Randomization occurs in the REDCap database using information gathered during the baseline interview (participant's depression and substance use scores). See the cover page of the baseline assessment for guidelines. This information can be directly entered into REDCap, which will then generate the allocation.

Follow-Up Assessment Schedule:

Follow-up assessments are conducted at 1-, 3-, 6-, 9-, and 12-months post-baseline. These assessments can be conducted remotely or in-person. All follow-up assessments are audio-recorded.

Measure	Self- Repo rt	1-Mo	3-Mo	6-Mo	9-Mo	12- Mo
Sociodemographics II		X	X	X	X	X
Health Questionnaire (PHQ-9)		X	X	X	X	X
Disclosure Scale (BHD & SSSES)		X	X	X	X	X
Disclosure List		X	X	X	X	X
Self-Rating Scale Item (SRSI)	X	X	X	X	X	X
Contemplation Ladder	X	X				
PROMIS Global Health	X	X	X	X		
Health Information	X	X	X	X	X	X
Well-Being Scale	X	X	X	X	X	X
Acceptance and Action Questionnaire-II (AAQ-II)	X	X	X	X	X	X
Multidimensional Scale of Perceived Social Support (MSPSS)	X	X	X	X	X	X
Berger HIV Stigma Scale	X	X	X	X	X	X
Healthcare System Distrust Scale	X	X	X	X	X	X

Everyday Discrimination Scale	X	X	X	X	X	X
Visit Specific Satisfaction Questionnaire	X	X				
Client Satisfaction Questionnaire-Revised	X	X				
End-of-Treatment Questionnaire	X	X				

I. REDCap ASSESSMENT DATABASE

This study uses a centralized REDCap database for all data collection and entry.

J. PROCEDURES FOR WITHDRAWAL OF CONSENT

If the participant communicates to research staff that they would like to withdraw their consent to be in the study at any point, the staff must document this in the Engage Tracking Log, and if possible, obtain written documentation from the participant via letter or in-person.

Once the participant has withdrawn consent, the staff no longer has permission to contact the participant regarding the study and will not review any electronic health record information about the individual.

K. PROCEDURE FOR WHEN PATIENT ENDORSES CURRENT SUICIDAL IDEATION/DISTRESS

The PHQ-9 should be administered early in the assessment so that a clinician can promptly respond. If a patient endorses current suicidal ideation at any time during any assessment, and/or as assessed by the PHQ-9 (i.e., score >0 on item #9) or otherwise in conversation, study staff will take the following steps:

- Immediately text a licensed study clinician to notify them that a risk assessment might be needed
- Administer the Modified Scale for Suicidal Ideation (MSSI) at the end of the assessment, unless the participant is in distress and interrupting the appointment is warranted
 - After collecting the MSSI information, explain to the individual that our study values our participants and wants to offer resources or help if needed.

- Ask who knows about the patient's suicidality (e.g., therapist, case manager). If there are providers who are aware of these issues, ask when the patient will speak to them next.
- Pause the assessment and call the study clinician (outside of the appointment room if conducting the assessment in-person). The clinician will then determine next steps based on the information gathered by the study staff.

If a patient endorses any homicidal ideation (HI) or violent ideation (VI) during the assessment, collect relevant information (frequency of thoughts, intent to act, plan, person/people in question) and report to on-call clinician to determine if patient is at imminent risk of harming others.

If a clinical check-in is completed, the staff will complete a note, to be stored in the research PHI folder, detailing:

- How the event was identified (e.g., follow-up appointment, phone call)
- Pertinent clinical information indicating risk
- Steps taken by the licensed clinical coverage staff to address the risk
- Yes/No contraindications to continuing in the study
- How symptoms will be monitored at the next visit

If a participant is evaluated within the study by a licensed member of the investigative team and it is determined that no additional clinical services are needed, then the note will suffice as a research chart note to be stored with the research study folder. If the participant is seen by a clinic staff right away, document information you gathered at that point, and that they have been transferred to their clinic for further evaluation. This would constitute an adverse event that PI will need to report to the IRB and NIMH. The research chart note for transferred patients will also be stored in the research PHI folder.

L. SAFETY REPORTING

All adverse events related to the participant that come to the staff's knowledge must be communicated to the PI immediately. He will then report to IRB and NIH, as appropriate.

Brief Acceptance-Based Retention Intervention for Newly Diagnosed HIV Patients

NCT04201288

Statistical Analysis Plan – 4/23/19

Data analytic plan (Aim 1).

We will use logistic regression to test the hypothesis that compared with ETAU, ABBT will increase the likelihood of meeting minimum DHHS recommended HIV care. To test the hypothesis that ABBT will result in improved virologic suppression, relative to ETAU, MANCOVA will be used. Planned baseline covariates include age, gender, race-ethnicity, HIV viral load, and study site. Any baseline variables associated significantly ($p < .10$) with subject attrition will also be included as covariates. We will also co-vary for cumulative TAU exposure. A 2-tailed probability of Type I error $< .05$ will be used for all null hypothesis tests.

We will use latent growth models (LGM) to estimate the effect of intervention on ART adherence, disclosure of HIV status, perceived social support, and HIV stigmatization. Data will be available from baseline, 1-, 3-, 6-, 9-, and 12-month follow-ups. This approach offers the flexibility to accommodate outcomes with a range of exponential family (e.g., normal, binomial, etc.) error distributions and allows a comparison of possible alternative growth processes (linear, quadratic, unconstrained with freely estimated time values) describing change over time. Initially, the Satorra-Bentler Scaled Chi-Square⁸⁵ will be used to compare linear change, quadratic change, and models with freely estimated time values. After identifying the best fitting unconditional LGM, conditional LGM models will be estimated in which the intercept and slope growth factors will be regressed on group, age, gender, race/ethnicity, and any baseline measures that significantly ($p < .10$) predict attrition. Significant differences in slope growth factors are consistent with the hypothesis that the ABBT and ETAU arms experience different patterns of change over time.

Data analytic plan (Aim 2).

The hypothesis that the effects of ABBT will be mediated by increased HIV acceptance and increased willingness to disclose HIV status will be tested in a latent growth model framework⁹¹. We will extend the LGMs estimated when testing the effects of ABBT on secondary outcomes (AIM 1). The slope growth factors in the LGM are latent variables that represent change trajectories which can be used to account for differences in more distal outcomes. For example, the likelihood of meeting minimum DHHS recommended HIV care.

Mediation is tested by specifying an indirect effect defined as the product of the effect of intervention on the slope growth factor of the hypothesized mediator (HIV acceptance, increased willingness to disclose) by the effect of the mediator on meeting DHHS recommended HIV care. Bias-corrected bootstrap resampling is generally recommended for testing the statistical significance of indirect effects⁹². Simulation studies have generally shown this method to be the most efficient method for testing mediational hypotheses^{64, 93}. Mplus⁸² statistical software has facilities to specify and estimate the LGM mediation models.

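### The SAP assigns virologic suppression to MANCOVA without stating coding, viral-load time points or tested effect; a yes/no status needs a logistic-type model with one prespecified signed contrast

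*SAP*

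**What the plan says.** The SAP, Data analytic plan (Aim 1), covers this outcome in one sentence: "To test the hypothesis that ABBT will result in improved virologic suppression, relative to ETAU, MANCOVA will be used". The covariates listed next include baseline viral load and study site. The error rate is two-sided at .05 for every test. The only provision bearing on missing data is "Any baseline variables associated significantly ($p < .10$) with subject attrition will also be included as covariates".

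The other binary Aim 1 outcome, receipt of recommended HIV care, is assigned to logistic regression in the same paragraph. The following paragraph plans latent growth models for adherence, disclosure, support and stigma, and says of them: "This approach offers the flexibility to accommodate outcomes with a range of exponential family (e.g., normal, binomial, etc.) error distributions". The follow-up months appear in that paragraph, which does not include viral load among its outcomes.

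The Protocol document is a manual of procedures. Its Introduction says "This MOP serves as a supplement to the protocol", so a further protocol exists that was not supplied. The follow-up table in section H lists no viral load by name. It does list an instrument titled Health Information, whose content is not shown. Section J says that once consent is withdrawn staff "will not review any electronic health record information about the individual", which suggests that records are reviewed for the other participants.

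**The concern.** The hypothesis is directional: "ABBT will result in improved virologic suppression, relative to ETAU". The method attached to it does not fix what is measured, when, or which comparison decides the question. Unless these are settled elsewhere, the coding, the visits and the tested effect remain open when the data are analysed.

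The method also fits poorly. Suppression ordinarily denotes a yes/no status, whereas MANCOVA assumes continuous, jointly normal outcomes. On untransformed viral load it would ignore skewness and values below the detection limit.

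MANCOVA normally means two or more dependent variables. If these are follow-up viral loads, two things follow. The standard analysis uses only participants with every value, so a participant with four of five viral loads contributes nothing. The multivariate group test asks whether the arms differ in any direction at any time point, so a significant result is not in itself evidence of better suppression. No effect measure is named to say by how much suppression differs.

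**Working it through.** **What is specified.** The documents give no sample size, suppression rate, missing rate or number of viral loads, so there is no planned figure to reproduce. The first check is textual.

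| Item | SAP | Protocol document |
|---|---|---|
| Threshold; yes/no or continuous | not stated | not stated |
| Viral-load time points and windows | not stated (months given only for other outcomes) | none named in the section H table |
| Effect tested (omnibus, average over time, group-by-time, single visit) | not stated | not stated |
| Effect measure | not stated | not stated |
| Participants with a missing viral load | attrition predictors added as covariates | record review ends at withdrawal of consent |

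A covariate adjusts the comparison among participants in the model. It does not bring back a participant whose outcome vector is incomplete.

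The three illustrations below rest on assumed inputs.

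**1. Share kept by a complete-case analysis.** Assume each of k viral loads is missing with probability m = 0.10.
- Independent missingness, share = (1 − m)^k: k = 2, 0.9² = 0.81; k = 3, 0.9³ = 0.73; k = 5, 0.9⁵ = 0.59.
- The same people miss every visit, share = 1 − m = 0.90 for any k. An all-available-data model then recovers nobody, because those excluded have no values.

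**2. Sign of the omnibus test.** Assume k = 3, 75 analysed per arm (n), between-visit correlation 0.6, unit SD and no covariates. For two groups the omnibus test is Hotelling's T², with noncentrality λ = (n/2) d′C⁻¹d and 3 and 146 degrees of freedom, where d is the vector of arm differences and C the correlation matrix.
- Benefit of 0.4 SD at every visit: d′C⁻¹d = 3 × 0.16 / (1 + 2 × 0.6) = 0.218; λ = 37.5 × 0.218 = 8.18; power 65.2%.
- Harm of 0.4 SD at every visit: the same λ, power 65.2%.
- Effects of +0.4, −0.4 and 0, which average zero: d′C⁻¹d = 0.32 / (1 − 0.6) = 0.80; λ = 30; power 99.8%.

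Rejection therefore does not distinguish benefit from harm or from a mixed pattern.

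**3. Cost of yes/no coding.** Assume one viral load, a latent normal shift between arms, and 80% power on the continuous scale. The noncentrality is (1.95996 + 0.84162)² = 7.849. The relative efficiency of dichotomising at suppressed proportion p is φ(z_p)² / [p(1 − p)].
- p = 0.50: efficiency 0.64; 7.849 × 0.6366 = 5.00; power = Φ(√5.00 − 1.96) = 61%.
- p = 0.85: efficiency 0.43; 7.849 × 0.4264 = 3.35; power = Φ(√3.35 − 1.96) = 45%.

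**The case against.** The strongest reply is that the case-dropping and the missing sign both need two or more follow-up viral loads, and no text says that there are. This stands: with one viral load the model is ANCOVA and both problems disappear. The unstated coding, time point and effect measure remain.

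Second, complete-case deletion is how MANCOVA is normally run, not a rule in the SAP. This also stands. A reader might infer that the plan discards every participant with a gap. The documents support only that handling of missing viral loads is unstated, that the named method excludes such participants by default, and that imputation is neither planned nor ruled out.

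Third, the missing-data evidence is thin. Section J concerns withdrawal only, and if viral loads come from health records, a missed interview need not mean a missing viral load. Withdrawal also removes all later values together, which is nearer to the pattern where little is recovered. Large losses need independent gaps at several visits, and nothing in the documents supports that.

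Fourth, a repeated-measures layout has a signed one-degree-of-freedom group test, and adjusted arm means would show direction. Both are true, but the SAP selects neither as the test.

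Finally, the separate protocol may supply the definitions. It may. The SAP does not refer to it for them.

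**Conclusion.** The concern holds as under-specification together with a method that does not suit a yes/no outcome. It should be fixed. Confidence is medium, because the governing protocol was not available and the intended layout is unknown.

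The two further consequences are conditional on several follow-up viral loads being analysed jointly. Under that condition the standard analysis excludes incomplete participants, and a significant omnibus result does not by itself show improvement.

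A reader might go further and infer that the trial will lose a large share of its power, or that its suppression result will be biased. The documents do not support either. Every percentage above rests on assumed inputs. The retained share runs from 59% to 90% at one assumed missing rate. The omnibus test is not always weaker than an averaged contrast: when the effect changes over time it can be stronger. Bias from complete-case analysis is possible but not shown.

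**What to change.** In the SAP, Data analytic plan (Aim 1):

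- Define suppression, including its threshold, and state which viral loads enter, with their time points and windows.
- Replace MANCOVA with logistic regression if one time point is used, or with a GEE or mixed logistic model on all available viral loads if several are. Adjust for baseline log viral load and the planned baseline covariates.
- Prespecify one signed arm contrast chosen for the clinical question, such as 12 months or the average over follow-up. Report an odds ratio or risk difference with its 95% confidence interval.
- If viral load is kept continuous, use a repeated-measures model on log viral load that handles values below detection.
- If the separate protocol already fixes any of these, cite it.

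The cost is SAP wording and slightly more analysis work, with no new data. There are three downsides:

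- Yes/no coding can cost power relative to log viral load: from 80% to about 61% or 45% in the third illustration.
- The mixed model relies on data being missing at random, and an unweighted GEE on a stronger assumption.
- Little is recovered if the same people miss every viral load.

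### REDCap allocates on baseline depression and substance use scores, but no SAP model commits to adjusting for them: a small power cost for the Aim 1 arm comparisons, and possible false-positive mediation in Aim 2

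*SAP*

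**What the plan says.** **Allocation.** Protocol, section H, Randomization: "Randomization occurs in the REDCap database using information gathered during the baseline interview", and the information meant is the participant's "depression and substance use scores". The paragraph adds: "This information can be directly entered into REDCap, which will then generate the allocation". It gives no cut-offs, block size or method, and refers staff to the cover page of the baseline assessment.

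**Logistic regression and MANCOVA.** SAP, Data analytic plan (Aim 1): "Planned baseline covariates include age, gender, race-ethnicity, HIV viral load, and study site". Cumulative TAU exposure is added. Baseline variables associated at p<.10 "with subject attrition will also be included as covariates".

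**Latent growth models (LGM).** Same section: "the intercept and slope growth factors will be regressed on group, age, gender, race/ethnicity, and any baseline measures that significantly" predict attrition, again at p<.10.

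**Mediation models.** SAP, Data analytic plan (Aim 2): "We will extend the LGMs estimated when testing the effects of ABBT on secondary outcomes". No allocation factor is added.

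**Dates.** The SAP is headed "Statistical Analysis Plan – 4/23/19"; the protocol document is dated 8/30/21.

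**The concern.** Variables that drive allocation would normally appear in the analysis model. Here they appear only if an attrition screen selects them, and that screen depends on the data, not on how patients were allocated. Two different things are at stake.

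- **Aim 1 arm comparisons.** If allocation balances the arms on prognostic scores, the estimated arm difference varies less from trial to trial than a model without the scores believes. The reported standard error is too large, the null rejection rate falls below 5%, and some power is lost.
- **Aim 2 mediation.** The indirect effect is the arm-to-mediator effect times the mediator-to-outcome effect. Randomization protects the first factor but not the second. If depression or substance use affects both the mediator's slope and care attendance, mediator and outcome are associated even when neither causes the other. Balance between arms does not remove this.

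**Working it through.** The documents give no sample size, effect size, event rate, prognostic strength or allocation method, so there is no stated figure to reproduce. Only the two-sided 5% level and the covariate lists come from the documents. Every other input below is an assumption.

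**1. Linear model, exact balance.** Let R2 be the share of residual outcome variance that the omitted scores explain. The model's standard error is too large by f = 1/sqrt(1 − R2). Then null rate = 2(1 − Φ(1.96f)). For a test designed for 80% power, power = Φ(2.80 − 1.96f).

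| R2 | f | 1.96f | Null rate | Power |
|---|---|---|---|---|
| 0 | 1.000 | 1.960 | 5.0% | 80.0% |
| 2% | 1.010 | 1.980 | 4.8% | 79.4% |
| 5% | 1.026 | 2.011 | 4.4% | 78.5% |
| 10% | 1.054 | 2.066 | 3.9% | 76.9% |

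**2. Logistic test.** Simulation with N=200, true log OR 0.90, overall response about 50%, two binary scores, permuted blocks of 4 within the four strata, the five named covariates in every model, Wald test, and 10,000 replicates per cell. Cumulative TAU exposure was not simulated. The attrition screen was run on simulated attrition of 20% to 23%, with outcomes kept for everyone.

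| Each score's OR | 1.0 | 1.5 | 2.0 | 3.0 |
|---|---|---|---|---|
| Power, scores always in | 86.7% | 86.5% | 85.7% | 82.7% |
| Loss (points), scores never in | 0.2 | 0.7 | 1.3 | 3.6 |
| Loss, p<.10 screen, scores unrelated to attrition | 0.2 | 0.6 | 1.1 | 3.2 |
| Loss, p<.10 screen, scores predict attrition as strongly as outcome | – | 0.5 | 0.5 | 0.2 |
| Null rate, never in | 5.5% | 4.9% | 4.8% | 3.6% |
| Null rate, always in | 5.6% | 5.3% | 5.5% | 5.0% |
| Power at exact 5% size, without / with | 85.3 / 85.4% | 85.9 / 86.0% | 84.9 / 84.7% | 82.3 / 82.6% |

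A score unrelated to attrition passes the screen about 10% of the time. In the related case it passes 31%, 62% and 92% of the time at OR 1.5, 2.0 and 3.0. A separate simulation with the same N, block size and log OR gave losses of about 0.3 points at OR 2 and 1.8 at OR 3.

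A simpler simulation (N=200, treatment OR 2.25, no other covariates, no attrition screen, not matched on size) gave larger losses: 74.7 − 72.6 = 2.1 points at OR 2 and 72.2 − 67.7 = 4.5 at OR 3. With blocks that ignored the scores, its null rate at OR 3 was 5.1%. The conservatism therefore comes from balancing on the scores.

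**3. Growth-model slopes.** Per-person slopes over 0, 1, 3, 6, 9 and 12 months, N=200, complete data; power without versus with the scores:
- scores affect level only: 76.1 vs 76.2%
- scores explain 5% of slope variance: 74.7 vs 75.6%
- scores explain 16%: 72.3 vs 76.0% (null rate 3.9 vs 4.8%; at equal size, power 76.3 vs 76.7%)

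**4. Mediation.** N=200, stratified blocks of 4, arm shifts the mediator by 0.5 SD, mediator has no effect on outcome, 4,000 runs. A joint-significance test stands in for the bias-corrected bootstrap.

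| Scores | False-positive mediation, without | With |
|---|---|---|
| Inert | 4.6% | 5.1% |
| OR 2, mediator shift 0.3 SD per score | 9.1% | 4.8% |
| OR 2, mediator shift 0.5 SD per score | 17.3% | 4.7% |

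A second run of the last two rows gave 9% vs 4% and 19% vs 5%. The baseline is as expected: the arm-to-mediator test has z = 0.5 × sqrt(200)/2 = 3.54 and power Φ(3.54 − 1.96) = 94%, and 94% × 5% = 4.7%.

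**The case against.** **The allocation method is unknown.** This stands. The protocol document never says stratified, blocked or minimized, and it describes itself as a supplement to a protocol that is not in the file. The Aim 1 effect needs balance on the scores. The Aim 2 effect does not.

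**The SAP partly covers it.** The covariate list is worded openly, the attrition screen can admit either score, and the SAP is about 28 months older than the protocol document, so this may be a matter of updating. All true. But the screen is no commitment, and a prognostic score unrelated to attrition would usually stay out.

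**The Aim 1 consequence is slight.** This stands too. The null rates of 4.9% and 4.8% at OR 1.5 and 2.0 cannot be told from 5% with 10,000 replicates (standard error about 0.22 points). At those strengths the adjusted Wald test runs slightly above 5%, so part of its apparent gain is excess size. At equal size the logistic difference disappears.

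**Stronger readings to avoid.** A reader might infer that omitting the allocation factors invalidates the primary test or inflates its type I error. The documents do not support that: for an arm comparison the error runs the safe way. A reader might equally infer that omission is on the safe side throughout the SAP. That fails for Aim 2, where the mediator-to-outcome path is observational.

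**Conclusion.** The mismatch between allocation and analysis is on the page. Its consequences differ by aim.

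- **Aim 1.** Slight conservatism, conditional on balance and prognostic value. The loss is about 0 to 1 point at score OR up to 2 and 2 to 4 points at OR 3, and somewhat more in a model with no other covariates. It is near zero if the scores are not prognostic, if they affect only level in the slope models, or if the screen brings them in. Type I error is not inflated.
- **Aim 2.** False-positive mediation can rise, illustratively to 9% to 19% against about 5% with the scores. This requires a score that affects both mediator slope and attendance, and an intervention that moves the mediator. The bootstrap itself was not simulated.

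All sizes rest on assumed inputs; the directions do not depend on the particular values. This is a nearly free improvement, with a small expected gain for Aim 1 and a possible validity gain for Aim 2.

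**What to change.** In the SAP, name the baseline depression and substance use variables, coded as REDCap uses them for allocation, as fixed covariates in:
- the logistic, virologic and latent growth models;
- both the mediator and the outcome equations of the mediation models.

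They should stay in whatever the attrition screen shows. State that the logistic odds ratio is then conditional on them.

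The cost is SAP wording and a few degrees of freedom. No new data are needed, because the scores are collected at baseline and entered before allocation. In Aim 2 this removes confounding by these two scores as coded, not by other common causes of mediator and outcome.
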